5 STUDY DESIGN

This study aims to determine if there are differences in the effectiveness and clinical outcomes of various conservative treatments offered to patients who suffer from triangular fibrocartilage complex (TFCC) tears. A four-arm (Section 2.4) factorial, randomised clinical trial will be implemented.

Participants will be randomly allocated to either an active control group or one of three intervention groups. Participants will be asked to complete an electronic questionnaire consisting of outcome measures designed for conditions specific to the hand and wrist. Outcome measures will be administered at baseline (pre-treatment); 6 and 12 weeks (primary end-point); and at 6, 12 and 24 months from baseline (secondary end-point). Compliance and complications will be recorded at all post-intervention intervals, including two weeks after treatment commencement.

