8.2 RANDOMISATION

Block randomisation will be performed to achieve balance in the allocation of participants to the different treatment arms throughout the course of the recruitment period. Fifteen blocks will be generated, with three multiples of each treatment arm per block. As a result, for every 12 randomly assigned treatment allocations, each intervention arm will have a comparable number of participants.

The randomisation sequence will be concealed in sequentially numbered sealed, opaque envelopes. The randomisation procedure will be administered by a research assistant who will not be blind to allocation for the duration of the study. They will open an envelope and reveal the allocation to the patient. As all treatment groups involve a hand therapy session, all participants will be provided with a referral for hand therapy by their referring surgeon when enrolled in the study. A dual randomisation procedure will be implemented, with one envelope opened at baseline and the other at the 6 week interval. At the baseline appointment, the assessor will open an envelope to reveal whether the participant will be receiving a splint.

A second randomisation will occur at 6 weeks to reveal whether the participant is to have a cortisone injection. Each envelope will contain a sheet of paper with the intervention group, as listed below.

Group A Hand Therapy (HT)	Group B HT + Splint	Group C HT + Cortisone	Group D HT + Splint + Cortisone
-------------------------------------	-------------------------------	----------------------------------	---

If randomly allocated into Group C or Group D, the participant's study surgeon will issue a referral for a cortisone injection to be administered at Brisbane Private Imaging, 6 weeks after the baseline appointment. The treating surgeon will not be blind to allocation to maintain standard medical care.

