8.4.3 Corticosteroid Injection

A single dose of ultrasound guided intra-articular corticosteroid injection will be provided by radiologists at Brisbane Private Imaging (Brisbane Private Hospital, Brisbane) at the 6 week interval. The steroid (Celestone Chronodose™) and local anaesthetic (Marcain™) combination to be administered, is the current hydrocortisone & local anaesthetic (HCLA) medication routinely used at Brisbane Private Imaging. A standard procedure will be followed:

1. Participant will be asked to lie in a supine position on the examination table with the affected wrist resting comfortably palm side down on the table or across their abdomen.
2. Antiseptic solution will be applied to the skin.
3. A 25 gauge, 38mm needle will be inserted into the dorsal aspect of the TFCC using ultrasound guidance.
4. A mixture of 1 mL of Celestone Chronodose and 1 mL of 0.5% Marcain will be injected into the TFCC.

The injections will be provided by radiologists at Brisbane Private Imaging, at the Brisbane Private Hospital. The treatment will be bulk billed for the participants (Appendix 14.7)

Celestone Chronodose™ (Merck Sharp & Dohme Pty Ltd, Australia) contains 1ml of betamethasone 5.7mg. It has full TGA approval (Appendix 14.8).

Marcaïn™ (AstraZeneca PTY Ltd, Australia) contains the active ingredient bupivacaine hydrochloride monohydrate. It has full TGA approval (14.9).

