8.5.1 Primary End-point

Participants will be assessed by their referring surgeon and have outcomes measured by a research assistant at 12 weeks to assess effectiveness of the randomised conservative treatment for treating the injury. Patients who demonstrate no benefit from conservative management, or an aggravation in symptoms may be considered for further conservative treatment or surgical intervention at the surgeon's discretion. Any further treatment received will result in the conclusion of the participant's ongoing study involvement. Assessments will be made at 2 and 6 weeks to monitor compliance to the treatment allocated, complications/adverse events and an interim assessment of treatment outcomes (6 weeks only).

Data Collection Interval	Range	Review Method
Pre-intervention/baseline	≤ 12 months post initial injury	In person at the clinic Surgeon + Researcher + Hand Therapist
2 weeks Compliance & complications	2 weeks +/- 5 days	In person at the clinic Researcher + Hand Therapist
6 weeks Interim Assessment	6 weeks +/- 10 days	In person at the clinic Researcher + Hand Therapist + Surgeon

12 weeks Primary End-Point	2 – 4 months	In person at the clinic Surgeon + Researcher
-------------------------------	--------------	---

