9.3 DATA ANALYSIS

Baseline demographic and clinical data will be reported using descriptive statistics and will be tabulated. Between groups differences in baseline data will be examined using unpaired conventional tests of hypothesis depending on the nature of the data. Between group and within group differences in outcome measures over time will be examined using a priori unpaired and paired conventional tests of hypothesis depending on the nature of the data. Linear mixed effects models will be used to examine the within and between group variability of the four groups. Bonferroni adjustments for multiple comparisons will be made where appropriate to mitigate risk of type-1 error.

The complication rates will be reported in terms of frequency. The frequencies of complications will be compared using statistical analysis such as the Pearson chi-square statistic.

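### The week-6 score is nominally pre-injection for cortisone, but the plan groups it with the primary end-point and does not separate the splint and cortisone phases

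*Protocol*

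**What the plan says.** **Timing of cortisone.** Protocol 8.2: "A second randomisation will occur at 6 weeks to reveal whether the participant is to have a cortisone injection". For Groups C and D the same section has the surgeon refer the participant "for a cortisone injection to be administered at Brisbane Private Imaging, 6 weeks after the baseline appointment". Section 8.4.3 also places the injection at the 6-week visit.

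**Status of week 6.** Section 5 gives the schedule after baseline as "6 and 12 weeks (primary end-point); and at 6, 12 and 24 months from baseline (secondary end-point". Section 8.5.1 describes the week-6 visit as "an interim assessment of treatment outcomes (6 weeks only". The project summary and the table in 8.5.1 name 12 weeks alone as the primary end-point.

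**Analysis.** Section 9.3 plans paired and unpaired tests of the outcomes over time, then adds: "Linear mixed effects models will be used to examine the within and between group variability of the four groups". It names no visits, contrast or covariates. Section 9.1 names a factorial ANOVA as the test behind the sample size.

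**The concern.** If the week-6 questionnaire is completed before cortisone allocation is known, then up to that point Group C has been treated exactly as Group A, and Group D exactly as Group B. Week 6 is then an outcome for the splint but a baseline for cortisone. The analysis section treats the four groups alike at every visit.

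Two things are at stake. First, four-group tests at week 6 could present chance differences between A and C, or B and D, as effects of an injection not yet given. Second, a group effect averaged over visits would mix a pre-injection visit into the cortisone estimate. Cortisone, alone or combined, is half of the primary objective (3.2.1), and the research question (3.1) turns on Group D, so this bears on the main conclusion.

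**Working it through.** **1. What has been received by each visit, taking 8.2 at face value**

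| Group | By week 6 | By week 12 |
|---|---|---|
| A | therapy | therapy |
| B | therapy + splint | therapy + splint |
| C | therapy (as A) | therapy + cortisone |
| D | therapy + splint (as B) | therapy + splint + cortisone |

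The true week-6 differences C-A and D-B are zero if the questionnaire comes before both the reveal and the injection. The protocol does not state that order. Section 8.4 also has radiology appointments arranged, where needed, after allocation at the baseline visit. Section 8.2 says that each envelope holds a sheet naming the group, from a list of all four. Either statement, read literally, could disclose cortisone allocation at baseline.

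**2. Chance findings at week 6.** With no true difference, testing C-A and D-B at the protocol's 0.05 gives at least one nominally significant result with probability 1 - 0.95² = 0.0975 per outcome. With Bonferroni over the two tests it is 1 - 0.975² = 0.049. Adjustment controls the rate but does not make the test meaningful.

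**3. The protocol's own sample size.** λ = f²N = 0.29² × 134 = 11.2694; numerator df 3, denominator df 130, critical F 2.6743, power 0.8013. With 25% attrition, 134/0.75 = 178.7, so 179, rounded up to 180. All reproduce.

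**4. Cortisone main effect.** I apply the same f = 0.29 to a 1-df contrast (d = 2f = 0.58). This is an assumption, since the protocol sizes a 3-df test. At 12 weeks alone with N = 134, power is 0.915, and 80% power needs N = 96.

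If weeks 6 and 12 are averaged, with no effect at week 6, the mean effect is halved and the SD is multiplied by √((1+ρ)/2). So f is multiplied by 0.5/√((1+ρ)/2). The protocol gives no week-6 to week-12 correlation ρ, so a range is assumed.

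| ρ | multiplier | effective f | power, N = 134 | N for 80% |
|---|---|---|---|---|
| 0.3 | 0.620 | 0.180 | 0.54 | 245 |
| 0.5 | 0.577 | 0.167 | 0.49 | 282 |
| 0.7 | 0.542 | 0.157 | 0.44 | 320 |
| 0.8 | 0.527 | 0.153 | 0.42 | 338 |

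**5. Averaging all five questionnaire visits after baseline.** One null visit in five leaves 0.8 of the effect if it persists to 24 months. The SD is multiplied by √((1+4ρ)/5), assuming equal correlations. Power is 0.98, 0.93 and 0.86 at ρ = 0.3, 0.5 and 0.7, against 0.915 for 12 weeks alone.

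**6. Contrast at 12 weeks, and the covariate.** A complete-data simulation (34 per group, ρ = 0.6 between all visits, true cortisone effect 0.58 SD at 12 weeks) gave:

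| Analysis | estimate | SE |
|---|---|---|
| 12 weeks, unadjusted | 0.58 | 0.173 |
| 12 weeks, baseline-adjusted | 0.58 | 0.138 |
| 12 weeks, baseline and week 6 | 0.58 | 0.129 |
| mean of weeks 6 and 12 | 0.29 | 0.153 |

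The algebra agrees. The residual SD factor is √(1 - 0.6²) = 0.80 with baseline only, and √(1 - 2 × 0.6²/1.6) = 0.74 with both scores.

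**The case against.** The strongest reply is that the protocol already fixes 12 weeks as primary in the summary and in the 8.5.1 table, and that the bracket in section 5 can be read as attaching to 12 weeks only. That largely stands: a reader might infer two primary time points, but the documents support only loose wording that needs reconciling.

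Next, a reader might infer that the planned model does dilute the cortisone effect. Section 9.3 never says that a group effect is averaged over visits, and the quoted sentence contains no error in itself. A group-by-visit model read at 12 weeks has no dilution. The choice of visits, contrast and covariates may properly sit in a statistical analysis plan that is not shown. This stands too, so the power loss is a risk that the wording permits, and the two-visit average is its worst case.

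Third, a reader might say that the trial wastes its best covariate. The plan neither uses nor excludes the week-6 score, and the gain beyond baseline adjustment is modest.

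Fourth, a zero week-6 difference by design cannot be taken as settled. In this open trial, if allocation were known at baseline, A-C differences at week 6 could reflect expectation or behaviour as well as chance. That stands, and it is a reason to fix the order of steps.

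The objection does not answer the mismatch itself: the protocol randomises in two stages and describes its analysis as if all treatments began together.

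**Conclusion.** The point holds as an inexpensive improvement. Week 6 is nominally pre-injection for cortisone, section 5 conflicts with the summary and the 8.5.1 table over its status, and section 9.3 does not separate the two phases.

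The size is conditional. If only weeks 6 and 12 were averaged, main-effect power would fall from 0.915 to about 0.42-0.54. This rests on f = 0.29 applied to a 1-df contrast, N = 134, no effect at week 6, and ρ assumed from 0.8 to 0.3. A 12-week contrast loses nothing. Averaging all five visits dilutes the effect by only 20% if it persists. Adjusting for week 6 as well as baseline cuts the SE from 0.138 to 0.129 at ρ = 0.6.

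The documents do not support saying that the trial will lose this power, or that a week-6 A-C difference must be pure chance.

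**What to change.** - In section 5, name 12 weeks alone as the primary time point.
- State that the week-6 questionnaire is completed before the second envelope is opened. Reconcile 8.4 and the envelope description with the week-6 reveal in 8.2.
- At week 6, compare the splint only (A+C against B+D). In any mixed model, constrain A = C and B = D at that visit. The constraint is justified only if the order above is followed.
- Estimate the cortisone main effect and the C-A and D-B contrasts at 12 weeks, adjusted for week-6 and baseline PRWHE.
- Estimate the splint effect and every contrast that includes the splint (B-A, D-A, D-C) with baseline PRWHE only. Week 6 is post-randomisation for the splint, and adjusting for it would remove part of the splint's own effect.

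The cost is two covariate sets to explain and a fixed order of steps within the week-6 visit. No participants, visits or measurements are added.

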10 DISSEMINATION OF FINDINGS

Findings from this investigation will be disseminated locally through existing state- and nationwide clinical networks and in-service education amongst relevant clinical teams (e.g. multi-disciplinary upper limb teams in hospital facilities).

Findings from this research will be disseminated widely through peer reviewed publications (e.g. The Journal of Bone and Joint Surgery) as well as through local, national and/or international conferences (E.g. Australian Hand Surgery Society, International Federation of Societies for Surgery of the Hand). The proposed wide dissemination of these findings is likely guide models of healthcare both nationally and internationally.

11 BUDGET AND FUNDING

11.1 STUDY RELATED COSTS

Item	Source	Details	Study Costs
Staff time	BHULRI	Protocol development, ethics, randomisation, study assessments, participant follow-up, data entry, analysis, writing paper for publication, submission.	In Kind (BHULRI) Research assistant time as part of MPhil degree
Corticosteroid Injection	Brisbane Private Imaging	Ultrasound guided Injection Participants to be bulk billed	Nil

		See agreement letter	
Hand Therapy	Extend Rehabilitation + EKCO Hand Therapy	Participants to pay at a subsidised cost of \$180 to the therapy clinic. This reduced rate is 50% of the normal fees charged.	Nil
Thermoplastic Splint	Extend Rehabilitation + EKCO Hand Therapy	\$70 per splint (90 participants)	\$6300
Vinyl dumbbells	Wholesaler	\$8 per 2kg weight, \$4 per 500g	\$700

11.2 FUNDING

The Brisbane Hand & Upper Limb Research Institute was awarded a \$7000 grant from the Queensland Hand Surgery Society for this project. These funds will be used to cover splinting costs for the 90 participants randomised to treatment Groups B and D. The remainder will be used to purchase vinyl dumbbells for participants to loan during the 12-week treatment period of study participation.

12 GLOSSARY OF ABBREVIATIONS

ADL	Activities of daily living
BHULRI	Brisbane Hand & Upper Limb Research Institute
DRUJ	Distal radioulnar joint
ECU	Extensor carpi ulnaris
GP	General practitioner
GRC	Global Rating of Change
HCLA	Hydrocortisone and local anaesthetic
ICC	Intraclass correlation coefficient
MCID	Minimal clinically important difference
PICF	Participant information consent form
PRWHE	Patient Rated Wrist Hand Evaluation
QuickDASH	Disabilities of the Arm, Shoulder and Hand Score short form
TFCC	Triangular fibrocartilage complex
UCL	Ulnar collateral ligament
VAS	Visual Analogue Scale

14 APPENDICES

14.1 PATIENT REFERRAL FORM

14.2 PARTICIPANT INFORMATION CONSENT FORM

14.3 CLINICAL EXAM FORM

14.4 PARTICIPANT ASSESSMENT QUESTIONNAIRE

14.5 HAND THERAPY AGREEMENT LETTERS

14.6 HAND THERAPY PROTOCOL

14.7 BRISBANE PRIVATE IMAGING AGREEMENT LETTER

14.8 TGA CELESTONE CHRONODOSE

14.9 TGA MARCAIN
